- c. **Leisure and CHAMPS physical activity scales¹³⁰** will be used to measure leisure and physical activities post-intervention. This will enable us to monitor lifestyle changes that may be related to C-REM.
- d. **Post-intervention questionnaire** will be administered to both groups to assess maintenance of blinding.
- e. **Health literacy questionnaires¹⁸⁹** will be given pre- and post-intervention in both groups. This will serve as a process measure for the efficacy of our health education intervention in the control group.

C.13. TIMELINE. We propose to screen and intervene in 210 subjects per group (assuming 20% attrition); 24-26 subjects will be randomized at a time into C-REM or health education programs (17 cycles over 54 months). We have recruited and evaluated larger samples in our other aging studies. Screening will start in month 2, and the interventions in month 4. A planned interim analysis by the DSMB (E.8.) will be conducted when 210 subjects are accrued (month 27 – Table 3). The final intervention group will have their post-intervention assessment in month 51. We will extend data collection to month 57 to enable us to collect outcomes to test durability till 12 months for the final intervention group. Detailed timetable with milestones and goals is in E.2.

C.14. DATA ANALYSIS.

Analytical Overview: Our goal in this preliminary RCT is to define the role of C-REM on improving simple and complex locomotion in sedentary frail seniors. Baseline distribution of covariates will be compared to assess adequacy of randomization to produce comparable groups of participants using appropriate graphical procedures and summary statistics.

C.14.1.a. Primary outcomes analysis: We will employ linear mixed effects model to compare the changes in gait speed and SPPB scores (P1) at post-intervention (week 9) as well as at 6 and 12 months post-intervention in C-REM versus controls.¹⁹³ The variance will be allowed to differ between C-REM and controls. The primary comparison between the two groups is post-intervention change in gait speed during NPW and WWT conditions and on SPPB. For WWT, we will also consider percent change in WWT speed from normal walking (*dual task cost*). We can define improvers on NPW and WWT by using cutscores on these measures as done in our pilot study (see C.14.2 and ref²⁶), and compare proportion of improvers vs. non-improvers in the two groups using generalized linear mixed effects models.¹⁹³

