The sample size (420) provides >80% power to detect clinically meaningful differences at significance level of 0.05. The conservative Bonferroni correction for multiple testing was used in sample size calculations. Based on conservatively estimated SDs of 12 cm/s, 20 cm/s and 1.5 points for NPW, WWT and SPPB, respectively, to detect clinically meaningful differences of 5 cm/s for NPW and 0.5 points for SPPB with 80% power,^{10, 11} and a conservatively estimated 10 cm/s for WWT (16 cm/s WWT speed improvement in our pilot study¹³), at least 169 subjects per group are needed. To take account the projected 20% drop out rate at end of intervention, 210 subjects per group will be enrolled.

5 cm/s is the minimal detectable intervention change that we can study with 80% power, and is not the maximal threshold of change expected after C-REM in this RCT. Any improvement >5 cm/s by C-REM will increase power. For instance, we observed **8 cm/s** improvement in our pilot study²⁶ ('substantial improvement' range^{136, 193}), which will provide us >90% power to test our hypothesis in this RCT.

Durability: Assuming cumulative dropout rates of 25% at 6 months, with n=210 per group, we will have 92%, 99% and 75% power for detecting differences of 5cm/sec, 10 cm/s and 0.5 points in NPW, WWT and SPPB, respectively. At 1 year of follow-up, assuming 30% cumulative dropout, we will have 90%, 98% and 72% power

for detecting differences of 5 cm/sec, 10 cm/s and 0.5 points in NPW, WWT and SPPB, respectively. If the difference in SPPB is substantial (1 point), the power will be more than 95% at both time points. However, given the lower power to reliably estimate SPPB change, we designate the durability examination as an exploratory aim. We will seek additional funding to extend examination of durability.

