➤ **Is our minimal detectable difference a clinical important difference?** We addressed clinical relevance of our estimate of change in multiple ways including validating effect size,⁵⁷ correlation with activity limitations, and expert opinion.^{78, 150} In the LIFE-P study, small clinical meaningful change in gait speed after a one-year PE intervention was 3-5 cm/s (substantial 8 cm/s).¹⁰ Perera et al recommended a 5 cm/s improvement in gait velocity as a small clinical meaningful change and 10 cm/s as substantial change over one year. We collaborated with Perera to develop clinical meaningful change estimates in gait velocity in our local population;⁵⁷ 4 cm/s was small meaningful change and 10 cm/s substantial change in one year.⁵⁷

Preliminary analysis in the Einstein Aging Study shows that a >4 cm/s gait speed improvement over one-year was associated with 13% reduced risk of activity limitations and 11% reduced risk of disability. Hence, the gait speed change selected is not only a statistically significant but also a clinically meaningful change in our population.

Direct extrapolation is limited as most previous studies report change over one year periods. In contrast, a 5 cm/s change or higher is predicted over only 8 weeks in this preliminary RCT.

C.14.2.a. Secondary outcomes: Quantitative gait variables other than speed (especially variability) and gait domains will be considered using linear mixed effects models as described above.¹⁹³ We will explore neurobiological mechanisms underlying C-REM by studying its effect on mobility related cognitive processes. With a sample size of 210 per group, assuming 25% and 30% cumulative dropout rate at 6 and 12 months, we can detect, with 80% power, differences of 0.29 and 0.30 SD units, in the change in each secondary outcome between C-REM and control at 6 months and 1 year.

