Reporting: All adverse events will be compiled and reported in summary form on an annual basis to the AECOM-CCI, and at the conclusion of the study. Unanticipated (non-serious) adverse events will be reported to the AECOM-CCI within 30 days via submission of an Adverse Event Report. Serious adverse events will be reported to the AECOM-CCI within 48 hours by phone, email or fax. A completed Adverse Event Report will be submitted within 10 days of initial notification. All deaths will be reported to the AECOM-CCI within 48 hours.

E.8.g. Recruitment Monitoring:

Process: The DSMB chair will assess the recruitment and retention of study subjects on an ongoing basis. The recruitment goal for this protocol is 420 subjects.

Reporting: Summary statistics regarding recruitment and retention of study subjects will be reported to the AECOM-CCI on an annual basis, and at the conclusion of the study.

E.8.h. Early Study Termination:

Process: Due to the non-invasive nature of the protocol, it is not expected that early termination will be required due to adverse events. However, constant monitoring of the participants by members of the DSMB, [name], other investigators, and research staff will be maintained to ensure that adverse events are not occurring. Early study termination will occur in the event of any unanticipated serious adverse event determined to be possibly, probably or definitely related to study procedures, failure to recruit at least 50% of the projected number of subjects within 4 months, or failure to retain at least 75% of study subjects to the conclusion of the protocol.

Early stopping rules: An interim look for monitoring both efficacy and futility is proposed after approximately half the total numbers of subjects (n=210) are screened and finish post intervention assessments.

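### E.8.h makes termination mandatory below 75% retention at an unnamed visit; if that visit is month 12, the dropout assumed in C.14 meets the criterion

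*Combined protocol and SAP*

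**What the plan says.** All references are to the combined protocol and SAP.

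- **E.8.h, Early Study Termination.** The list of triggers opens with "Early study termination will occur in the event of" and ends with "failure to retain at least 75% of study subjects to the conclusion of the protocol". The wording is mandatory. No section says which visit concludes the protocol or who counts as retained.
- **E.8.g, Recruitment Monitoring.** The DSMB chair follows recruitment and retention throughout the trial. E.8.e adds DSMB meetings every six months.
- **C.14.1.b, Power for primary outcome.** Enrolment is 210 per group, set as follows: "To take account the projected 20% drop out rate at end of intervention". For durability, the plan works with 25% cumulative dropout at 6 months and then "At 1 year of follow-up, assuming 30% cumulative dropout". C.14.2.a repeats both: "assuming 25% and 30% cumulative dropout rate at 6 and 12 months".
- **C.12.** The last scheduled outcome assessment is at 12 months.
- **C.13.** There are 17 cycles, interventions start in month 4, and the final group's post-intervention assessment is in month 51.
- **E.1 and C.15.b.** Subjects who become non-ambulatory stay in the study by telephone and mail, and telephone data are collected from dropouts.

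**The concern.** A mandatory stopping threshold should not be reachable simply because the trial behaves as its planning figures assume. Here a 75% floor stands beside a 12-month planning value of 70% retained, and the text does not say whether the floor applies at that visit. The same attrition therefore passes comfortably or fails clearly, depending on an undefined phrase.

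The 12-month visit serves an aim the plan treats as secondary in importance ("we designate the durability examination as an exploratory aim"). Attrition there could formally oblige the DSMB to end the trial. Because retention is watched as the trial proceeds, it could also become clear that the criterion will be met while some subjects still await the week-9 primary assessment.

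**Working it through.** **1. Are the C.14 dropout rates really the ones in use?** Inputs from C.14.1.b: SDs of 12 cm/s (NPW), 20 cm/s (WWT) and 1.5 points (SPPB); differences of 5 cm/s, 10 cm/s and 0.5 points; n = 210 × (1 − dropout) per group. The Bonferroni divisor is not stated. A two-sided alpha of 0.025 (divisor 2) reproduces the printed figures and is my inference. Power comes from the two-sample t test with noncentrality δ / (σ√(2/n)).

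| Visit | n per group | Recomputed NPW / WWT / SPPB | Stated |
|---|---|---|---|
| 6 months, 25% dropout | 157 | 92.4 / 98.5 / 75.8% | 92 / 99 / 75% |
| 12 months, 30% dropout | 147 | 90.6 / 97.9 / 72.7% | 90 / 98 / 72% |

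All six agree within one point, so 25% and 30% are the operative durability assumptions.

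**2. Retention against the floor.** The limit is 0.75 × 420 = 315.

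- End of intervention: 0.80 × 420 = 336; 336 − 315 = +21.
- 12 months: 0.70 × 420 = 294; 294 − 315 = −21.

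If each subject is retained independently at these rates (binomial, 420 subjects), the chance of finishing below 315 is about 0.5% at end of intervention and 98.7% at 12 months.

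**3. When does 315 become unreachable?** 420 − 106 = 314, so the 106th loss settles it. My assumptions are:

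- 17 equal cycles of 420/17 = 24.7 subjects, starting at even intervals from month 4 to month 49 (51 − 2), so 45/16 = 2.81 months apart;
- dropout rising linearly within each cycle from 0 to 20% at 2 months, 25% at 6 months and 30% at 12 months, counted from the start of the cycle.

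At month 46, 15 cycles have started. Eleven are past 12 months (11 × 0.30 = 3.30). The other four stand at 0.292, 0.269, 0.243 and 0.208, which sum to 1.012. Expected losses are (3.30 + 1.012) × 24.7 = 106.5. The 106th loss falls at about month 45.5.

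If the 6- and 12-month visits are counted from the end of intervention instead, it falls at about month 46.4. Hence about months 45 to 47. If losses are booked only when a visit is missed, it is about months 47 to 48. All of these precede month 51. At month 46 two cycles, about 49 subjects (2 × 24.7), have not reached week 9.

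**The case against.** The best case for leaving the text alone has four parts.

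- **The later rates are assumptions, not forecasts.** Only the 20% is called projected; the 25% and 30% are inputs to durability power. A floor stricter than a power assumption is not in itself a contradiction. This stands, and it is why the conclusion is conditional.
- **Retention and outcome data are different quantities.** C.14 dropout reduces the number with gait or SPPB results. E.8.h counts subjects retained, and E.1 keeps some people in the study without a gait result. This stands too: the shortfall of 21 needs both the 12-month reading and the C.14 sense of *retained*.
- **An end-of-intervention reading is available.** C.13 sizes the trial on 20% attrition, and C.15.f mentions the stopping rules close to the 20% over-enrolment. That reading is arguable, but the words of E.8.h point at least as readily to the last scheduled visit.
- **The DSMB may have settled the terms.** E.8.c has it draw up operating procedures at its first meeting, and these are not in the documents. Possible, but E.8.h as it stands defines neither term.

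Some stronger inferences are not supported. A reader might conclude that no time of checking is given; E.8.g provides for continuing assessment. A reader might add a 6-month reading, where retention would sit exactly on the limit; nothing in the text makes that visit the conclusion when 12-month visits are scheduled. A reader might take the amendment forms' silence to mean the DSMB left the terms undefined; the forms do not show that.

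In the other direction, a reader might think a 75% floor at end of intervention fits the sizing. It does not: 0.75 × 210 = 157.5 per group, below the 169 that C.14.1.b requires.

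**Conclusion.** The point holds in conditional form. If the protocol concludes at the 12-month visit and *retained* means not dropped out as in C.14, attrition at the assumed 30% leaves 294 subjects, 21 short of the 315 that E.8.h demands, and termination is mandatory as worded. On the end-of-intervention reading, the projected 20% leaves 336 and the criterion is not met.

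A reader might infer that the trial is bound to stop, or that the week-9 comparison will be lost. The documents do not support that. It would require the 12-month reading, the C.14 sense of *retained*, the assumed rates occurring, and a DSMB that acts once the floor is out of reach rather than at the end. The opposite comfort, that the primary comparison is safe because 12-month retention is known only afterwards, is not supported either: under the assumptions shown, the floor is out of reach at about months 45 to 47, before month 51. Those months rest on even cycle spacing and linear dropout, neither of which the plan states.

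**What to change.** Reconcile E.8.h with C.14 so that attrition at the rates the plan assumes cannot by itself meet a mandatory termination criterion. Either tie the retention criterion to a named visit where the two agree, or make its threshold consistent with the dropout assumed at the visit it refers to. Which of these is adopted is for the sponsor and the DSMB. In either case, state whether people followed only by telephone or mail (C.15.b, E.1) count as retained.

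The cost is a few words in E.8.h. Sample size and primary analysis do not change.

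Separate and minor: C.13 says collection to month 57 covers 12-month durability for the final group. That group is assessed post-intervention in month 51, and 51 + 6 = 57. Its 12-month visit would fall in month 63 (51 + 12), or about month 61 (49 + 12) if counted from baseline. E.2 already limits durability to month 57, so only the C.13 clause needs correcting.

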1.0 General Information

The version you are using is: August 2017

2.0 Amendment Information

2.1 Select the modifications being made below:

- Change in PI
- Change in key personnel and study contacts
- Changes to IRB Application
- Changes to or addition of new informed consent documents
- Changes to or addition of other study documents (protocol, investigator brochures, questionnaires, protocol, investigators brochure, recruitment materials, instruments, case report forms, study handouts or other miscellaneous documents)
- Adding external funding (grant application must be uploaded and the IRB application must be updated)

2.2 Provide a brief summary of the changes:

Added a new recruitment strategy to the application including to include recruitment of participants who have participated in other studies, but are not currently involved in another research project.

**If this is a sponsored amendment, and the sponsor has provided a document with a summary of changes, provide a summary of the key changes in the space above (i.e., administrative changes to the protocol, corrected protocol regarding test X and updated the consent document accordingly, etc.). The IRB cannot accept "see attached". The IRB also cannot accept just a copy of the list of changes instead of a summary.*

***For the addition of key personnel, please also indicate whether the individual(s) added will be conducting the informed consent process.*

2.3 Provide a justification for the amendment.

We will be recruiting participants who have completed the study protocol #2016-7153.

2.4 For an amendment generated by a study sponsor, provide the amendment version information, e.g. "Amendment #2 dated 11August2011".

This information will be used in the approval letter for the amendment.

2.5 Did the amendment originate from a drug company, a national study group, etc.? If "Yes," a copy of the correspondence must be attached to this amendment application.

Yes No

3.0 IRB Application Revision

Instructions:

1. Click on the grey bar labeled "Click here to attach the application." A new window will open up.
2. Click on "Add Revision" on the right and then click on "OK" on the popup window.
3. Make the revision to the relevant section of the application. Click "Save and Continue to Next Section" after every application section until you get to the very end of the application. If you are given the option to convert your application to a newer version, you must do so before completing your submission.
 - a. If you convert to the newest version of the application all but the first three sections of the application will disappear. Click on "Save and Continue to Next Section" after each section to recreate the application. You may need to answer new questions.
4. Once the application has been completely revised, you will then be sent back to the "Attach Study Application" page and the study application listed will have a new version number (i.e., version 1.2). Click on "Save Attachment".

Edit/ View	Version	Title
	1.15	Human Research Application (Version 1.15) - Attached

4.0 Study Document Revision or Addition

Study documents include the protocol, grant application, investigator brochures, questionnaires, recruitment materials, instruments, case report forms, study handouts or other miscellaneous documents.

To revise approved study documents, create a REVISED copy of the document in iRIS in order for the system to properly VOID the previously approved study document. Do NOT attach new documents unless they are for types of study documents that have never been previously approved.

GUIDANCE ON REVISING DOCUMENTS IS AVAILABLE IN THE AMENDMENT HANDBOOK IN THE HELP MENU.

Version	Title	Category	Expiration Date	Document Outcome	Checked Out	View Document
1.6	Protocol	Protocol		Approved		 974.97 KB

Only the following types of files may be uploaded into iRIS: .doc, .docx, .rtf, .txt, .pdf. The use of other file formats may delay IRB review and approval of your submission.

Protocol Requirements and Recommendations

1. The IRB requires that revised protocols have a version number and/or version date on the protocol document.
2. The IRB strongly recommends that revised protocol have page numbers.

3. The IRB must have a complete and up-to-date version of the protocol on record at all times. You may not upload additions to the protocol instead of a complete revised document. You may, however, upload only a tracked changes version of the protocol.

Other Study Document Recommendations

1. The IRB strongly recommends that if you have more than one similar study document (e.g. ads for different populations), distinguish between the documents using footers or other clear text in the document. Do not use the header function, since iRIS stamps documents in the upper right-hand corner.

Document Revision Requirements

1. If both the old version and the new version are Word documents, you may upload only a clean version of the new document.
2. If either the old version or the new version is a PDF file, you must also upload a tracked changed version or a document with the list of changes.

I understand that incorrectly uploading revised study documents will result in a delay of IRB review and approval.

1.0 General Information

The version you are using is: 12 February 2015 version C

1.2 For all studies migrated from PATS or West Campus/paper:

Amendments may NOT be submitted before a Migration Completion Form has been approved by the IRB. If your Migration Completion Form has not been approved, this amendment will be rejected by the IRB.

Questions? Please contact [contact].

2.0 Amendment Information

2.1 Select the modifications being made below:

- Change in PI
- Change in key personnel and study contacts
- Changes to IRB Application
- Changes to or addition of new informed consent documents
- Changes to or addition of other study documents (protocol, investigator brochures, questionnaires, protocol, investigators brochure, recruitment materials, instruments, case report forms, study handouts or other miscellaneous documents)

2.2 Provide a brief summary of the changes:

We will be identifying potential participants for recruitment by accessing medical/clinical records without consent.

**If this is a sponsored amendment, and the sponsor has provided a document with a summary of changes, provide a summary of the key changes in the space above (i.e., administrative changes to the protocol, corrected protocol regarding test X and updated the consent document accordingly, etc.). The IRB cannot accept "see attached". The IRB also cannot accept just a copy of the list of changes instead of a summary.*

***For the addition of key personnel, please also indicate whether the individual(s) added will be conducting the informed consent process.*

2.3 Provide a justification for the amendment.

We are planning to get a list of patients from Clinical Looking Glass who are patients at the Montefiore Geriatrics Ambulatory Practice to mail recruitment letters to and follow-up with a telephone screening interview using the same recruitment letter and screening procedures that are already approved.

2.4 For an amendment generated by a study sponsor, provide the amendment version information, e.g. "Amendment #2 dated 11August2011".

This information will be used in the approval letter for the amendment.

2.5 Did the amendment originate from a drug company, a national study group, etc.? If "Yes," a copy of the correspondence must be attached to this amendment application.

Yes No

3.0 IRB Application Revision

Instructions:

1. Click on the grey bar labeled "Click here to attach the application." A new window will open up.
2. Click on "Add Revision" on the right and then click on "OK" on the popup window.
3. Make the revision to the relevant section of the application. Click "Save and Continue to Next Section" after every application section until you get to the very end of the application. If you are given the option to convert your application to a newer version, you must do so before completing your submission.
 - a. If you convert to the newest version of the application all but the first three sections of the application will disappear. Click on "Save and Continue to Next Section" after each section to recreate the application. You may need to answer new questions.
4. Once the application has been completely revised, you will then be sent back to the "Attach Study Application" page and the study application listed will have a new version number (i.e., version 1.2). Click on "Save Attachment".

Edit/ View	Version	Title
	1.14	Human Research Application (Version 1.14) - Attached

